3.1.1.2 Dose escalation after at least 3 months of treatment

- In addition to the criteria in Section 3.1.1.1, any other clinically important manifestation of LAL Deficiency on either clinical examination, laboratory assessment, or imaging which has either
 - not improved from baseline
 - o improved and plateaued but has not normalized
 - (Note: The definition of a plateauing of effect requires consideration of a minimal of 3 assessments)
 - o failed to normalize within 12 months of initiation of treatment

Manifestations include but are not restricted to the following: A decrease in weight for age defined as crossing ≥ 2 major centile lines on standard weight for age curves, serum transaminases, albumin <3.5 g/dL, hepatomegaly, splenomegaly or lymphadenopathy. If the subject continues to have criteria for dose escalation after at least 4 infusions at a dose of 3 mg/kg qw, the Investigator may request of the Sponsor (in consultation with the Safety Committee) to increase the dose up to a maximum of 5 mg/kg qw on a case by case basis. In rare circumstances, a dose escalation to 5 mg/kg may be considered prior to 4 infusions, if

3.2 Rationale for Study Design

agreed to by the Sponsor and SC.

3.2.1 Dose Selection

Refer to Section 1.5.1 for the dose selection rationale.

3.2.2 Outcome Variable Selection

3.2.2.1 Safety

The safety and tolerability of treatment with sebelipase alfa, administered by IV infusion, will also be evaluated in this study. An ongoing study in infants with rapidly progressive LAL Deficiency, LAL-CL03, was designed to confirm a survival benefit in subjects who present with growth failure prior to 6 months of age. As that was the first study in infants with rapidly progressive LAL Deficiency, dosing was initiated with 2 once weekly doses at 0.35 mg/kg prior to allowing escalation to 1 mg/kg. Based on favorable safety data at 1 and 3 mg/kg in both infants and adults with LAL Deficiency, and the observed rapidly progressive presentation of the disease, this study is designed to initiate therapy at a 1 mg/kg weekly dose. In addition, because this study does not require confirmation of growth failure for entry, treatment may be initiated at a slightly earlier age than previously experienced in LAL-CL03. Thus, an important objective for this study is to confirm safety of initiating therapy at 1 mg/kg weekly in subjects at the earliest age at which diagnosis of rapidly progressive LAL Deficiency is confirmed.

Endpoints for safety of sebelipase alfa in children with LAL Deficiency will include:

- Incidence of AEs, SAEs, and IARs
- Changes from baseline clinical laboratory tests
- Changes in vital signs during and post-infusion, relative to pre-infusion values
- Physical examination findings
- Use of concomitant medications/therapies
- Characterization of ADAs, including ADA positivity rate, time to ADA positivity, median and peak ADA titer, and time to peak ADA titer.

Given the potential for ADAs to alter the safety profile of sebelipase alfa, the impact of ADAs on safety endpoints will be explored. Further characterization of ADAs, including inhibitory and/or neutralizing ADAs and measurement of specific ADA subtypes (e.g., IgE), may be performed, if appropriate.

3.2.2.2 Efficacy

The study is designed to confirm the efficacy of treatment with sebelipase alfa in subjects with rapidly progressive disease presenting in infancy. Survival endpoints will include proportion of subjects surviving to 12, 18, and 24 months of age, and other timepoints, as data permit, and estimated median age at death. Survival rates and median age at death derived from this study will be compared to rates/times reported in the literature and previous studies.

Subjects with LAL Deficiency presenting in infancy typically stop growing and this growth failure, in addition to being the predominant clinical feature, is also one of the main contributors to mortality. Improvement in growth is anticipated to be a prerequisite for any beneficial effects of sebelipase alfa on survival. Therefore, efficacy endpoints will include changes from baseline in the following growth parameters:

- Percentiles and/or z-scores, based on WHO child growth standards (WHO Multicentre Growth Reference Study Group, 2006 and 2007), for the following parameters:
 - Weight-for-age (WFA)
 - o WFL or WFH
 - LFA or HFA
 - Head circumference-for-age (HCFA)
 - Mid-upper arm circumference-for-age (MUACFA)
- Dichotomous growth status indicators for underweight, wasting, and stunting based on WFA, WFL/WFH, and LFA/HFA, respectively (UNICEF, 2009)

Note: Given the switch at age 2 years from measurement of length to measurement of height, growth parameters include weight related to both length and height and age related to both length and height.

A successful therapy for LAL Deficiency presenting in infancy should also mitigate the liver and hematological changes associated with the disease. Therefore, the following laboratory parameters will also be included as efficacy endpoints:

- Changes from baseline in aspartate aminotransferase [AST] and ALT levels
- Normalization of hemoglobin levels without requirement for blood transfusion
- Changes from baseline in serum ferritin levels

Additional exploratory efficacy parameters will be investigated to provide supportive evidence of an improvement of LAL Deficiency with sebelipase alfa treatment, and will include changes or percent changes from baseline (or first available assessment if baseline data are unavailable) in:

- Alkaline phosphatase, gamma glutamyltransferase (GGT), albumin, and bilirubin (direct, indirect, and total)
- Liver and spleen size/volume, as measured by ultrasound or magnetic resonance imaging (MRI)

- Hepatomegaly and/or splenomegaly (abdominal girth, liver size, and spleen size) by physical examination
- Platelet levels
- Serum lipid levels (total cholesterol, triglycerides, high density lipoprotein [HDL], and LDL)

Because LAL Deficiency presenting in infancy is rapidly progressive and patients often die within 6 months of age (Assmann, 2001, *The Metabolic and Molecular Basis of Inherited Disease*), information on development is limited in this patient population. The potential extended life expectancy in subjects receiving long-term treatment with sebelipase alfa provides an opportunity to develop an understanding of the developmental process in infants with LAL Deficiency treated with sebelipase alfa. To this end, the study will include an exploratory analysis of developmental outcomes, as assessed by the total and functional area scores on the Denver II developmental screening test.

Given the potential for ADAs to alter the PD effect of sebelipase alfa, the impact of ADAs on efficacy endpoints will be explored.

3.2.2.3 Pharmacokinetics

The C_{max} of sebelipase alfa in infants with rapidly progressive LAL Deficiency will be characterized in this study, blood volume permitting. The impact of ADAs on sebelipase alfa C_{max} will also be explored, if data permit.

3.2.2.4 Exploratory Biomarkers

Blood samples will also be collected to support exploratory analyses of changes or percent changes from baseline in potential disease-related biomarkers, which may be identified based on emerging information from the sebelipase alfa development program and scientific literature.

3.2.3 Study Duration

The duration of each subject's treatment in the study is expected to be at least 18 months, and subjects may continue to receive treatment in the study for up to up to 3 years. Therefore, the overall duration of a subject's participation in the study, inclusive of a 3-week screening period and a 4-week follow-up period, may be up to 3 years and 7 weeks.

4 Study Population

4.1 Target Population

The target population for this study is infants with rapidly progressive LAL Deficiency.

4.2 Number of Subjects

In light of the extremely low prevalence of the target disease, up to 10 subjects will be enrolled in the study.

4.3 Inclusion Criteria

A subject must meet all of the following criteria to be eligible to participate in this study:

- 1. Subject's parent or legal guardian (if applicable) consents to participation in the study.
- 2. Confirmation of documented decreased LAL activity relative to the normal range of the lab performing the assay or a documented result of molecular genetic testing confirming a diagnosis of LAL Deficiency..
- 3. Substantial clinical concerns, in the opinion of Investigator and Sponsor, of rapid disease progression requiring urgent medical intervention including, but not restricted to, the following:
 - a. Marked abdominal distension and hepatomegaly
 - b. Failure to thrive as evidenced by:
 - i. Weight for height is 2 or more SD below the mean for gender and age
 - ii. Weight curve has crossed downward by more than 2 major percentile lines on the WHO growth curves (1st, 3rd, 5th, 10th, 25th, 50th, 75th, 90th, 95th, 97th, 99th) after having previously achieved a stable pattern of growth
 - Disturbance of coagulation (e.g., requirement for FFP; two values of PT >15 sec, or PTT > 40 sec)
 - d. Severe anemia (e.g., requirement for blood transfusion or hemoglobin < 8 g/dL)
 - e. Sibling with rapidly progressive course of LAL Deficiency

4.4 Exclusion Criteria

A subject who meets any of the following criteria will be ineligible to participate in the study:

- Clinically important concurrent disease or co-morbidities which, in the opinion of the Investigator and Sponsor, would interfere with study participation, including, but not restricted to:
 - a. Additional severe congenital abnormality
 - b. Presence of severe infection that requires treatment with parenteral anti-infective treatment within the past 14 days
 - c. Previous history of circulatory collapse requiring inotropic support for more than 48 hours

Page 30 of 66

- d. Congestive heart failure
- e. Acute or chronic renal failure
- f. Other extenuating circumstances such as life-threatening under nutrition or rapidly progressive liver disease
- 2. Subject will be > 8 months of age at the time of first dosing.
- 3. Subject has received an investigational medicinal product other than sebelipase alfa within 14 days prior to the first dose of sebelipase alfa in this study.
- 4. Myeloablative preparation, or other systemic pre-transplant conditioning, for hematopoietic stem cell or liver transplantation.
- 5. Previous hematopoietic stem cell or liver transplant.
- 6. Known hypersensitivity to eggs.

4.5 Concomitant Medication and Treatment

A concomitant medication is any drug or substance taken during the study after the informed consent is signed. Any concomitant medications (including over the counter medications, herbal medications, preventive vaccines, vitamins and food supplements), treatments and procedures (including parenteral feeds, surgery, or physical therapy) received by the subject through completion of the follow-up visit, approximately 30 days after the last dose of IMP, must be recorded in the electronic case report form (eCRF). A description of the type of drug or procedure, the amount, duration, reason for administration of drug and the outcome of any procedure must be documented. Adverse events related to the administration of a concomitant medication or the performance of a procedure must also be documented on the AE page of the eCRF.

4.6 Discontinuation of Subjects from Treatment or Assessment

4.6.1 Premature Withdrawal from Study Participation

In accordance with the Declaration of Helsinki, subject's parent or legal guardian have the right to withdraw their child from the study at any time for any reason. The Investigator and Sponsor also have the right to withdraw subjects from the study at any time. A subject will be considered to have completed if they withdraw from the study.

Specific reasons for discontinuation may include but are not restricted to the following:

- Intercurrent illness
- Medically significant AEs
- Protocol deviation or non-compliance
- Termination of the study by the Sponsor

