4.6.2 Procedures for Discontinuation

A subject's parent or legal guardian is free to withdraw consent and/or discontinue the subject's participation in the study at any time, without prejudice to further treatment. A subject's participation in the study may also be discontinued at any time at the discretion of the Investigator or Sponsor.

Should a subject's parent or legal guardian decide to withdraw consent, all efforts will be made to complete and report the observations as thoroughly as possible. The parent or legal guardian of subjects who are discontinued from the study should be asked about the reason(s) for their discontinuation and about the presence of AEs. The date and the reason for discontinuation will be recorded in the eCRF. Subjects who discontinue prior to IMP administration will be replaced.

Subjects who are prematurely withdrawn from the study will be asked to complete all discontinuation assessments prior to withdrawal (see Appendix A), if possible. Information on the survival of discontinued subjects will be collected until completion of the study. Serious AEs will be followed according to Section 7.2.3 and reported according to Section 7.4. A subject will be considered early terminated if the subject does not complete the study after enrollment. A subject will be considered discontinued due to an AE if the subject received any infusion or partial infusion of the investigational medicinal product, but did not complete the study because of an AE, whether or not considered drug related. At the end of the subject's participation in the study, the Investigator will document the reason(s) for study discontinuation in the eCRF.

In the event that a subject dies, permission will be sought (through a separate informed consent form) from the subject's parent or legal guardian for an autopsy. Samples collected from these procedures will be used to further understand LAL Deficiency and the effect of sebelipase alfa.

When a subject fails to return for scheduled assessments, the following efforts should be made to contact his/her parent or legal guardian to determine a reason for the failure to return: 3 attempts, including the date and time, to be documented in the subject's chart. If there is no response, a certified letter should be sent. After these efforts have been exhausted, a subject should be identified as lost to follow-up in the eCRF.

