Final analyses will be performed after all subjects have completed treatment in the study (up to 3 years) or have died or withdrawn from the study.

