8.2 Determination of Sample Size

Up to 10 subjects who meet the requirements for inclusion will be enrolled in this study. No formal hypothesis testing is proposed in this study; all summary measures, including p-values, are considered descriptive.

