8.5 Subject Disposition

Data from all subjects who are consented will be included in the summary of subject disposition. The frequency and percentage of subjects who are consented for, treated in, discontinued from, and complete the study, along with reasons for discontinuation, will be summarized.

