# 7.1. Study Subjects

#### 7.1.1. Disposition of Subjects

Subject disposition will be presented in a listing, and will include age, gender, date of consent, date and dose of first infusion of study drug, date and dose of last infusion of study drug, date of completion or premature discontinuation from the study, and reason for discontinuation if the subject discontinues prematurely. Data from all subjects who signed the informed consent will be included in the summary of subject disposition. The frequency and percentage of subjects who are treated in the study, completed the study, and discontinued from the study, along with reasons for discontinuation, will be summarized. In addition, the number of subjects in the FAS will be presented.

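### Protocol 4.6.1 counts a subject who withdraws as having completed, which contradicts Protocol 4.6.2 and Section 8, and the SAP does not say who is a completer

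*Protocol*

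**What the plan says.** **Protocol 4.6.1** (premature withdrawal) gives parents, the investigator and the sponsor the right to withdraw a child, and then says: "A subject will be considered to have completed if they withdraw from the study". It goes on to list reasons for discontinuation, including medically significant AEs and termination of the study by the sponsor.

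**Protocol 4.6.2** (procedures for discontinuation) says: "A subject will be considered early terminated if the subject does not complete the study after enrollment". It also requires that "The date and the reason for discontinuation will be recorded in the eCRF". It defines discontinuation due to an AE as having received at least part of an infusion and then not completing the study because of an AE. Loss to follow-up is a separate eCRF classification.

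**Protocol Section 8** times the final analysis "after all subjects have completed treatment in the study (up to 3 years) or have died or withdrawn from the study".

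**Protocol 8.5** summarizes "subjects who are consented for, treated in, discontinued from, and complete the study, along with reasons for discontinuation".

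**SAP 7.1.1** plans the same kind of table: "The frequency and percentage of subjects who are treated in the study, completed the study, and discontinued from the study", with reasons for discontinuation. It adds a listing that gives each subject's date of completion or of premature discontinuation, with the reason if premature.

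Neither disposition section defines a completer. SAP 4.1, which lists departures from the protocol, does not mention the 4.6.1 rule.

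**The concern.** The 4.6.1 sentence is the only explicit statement in either document of who counts as completed, and it sits in an operative section. Someone programming the disposition table who looks for the definition will find this one. It makes withdrawal a form of completion, while the rest of the plan treats withdrawal as the opposite of completion.

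Two outputs are exposed. The first is the completed row of the disposition table, which readers use to judge retention in an uncontrolled study with treatment for up to 3 years. The second is the count of discontinuations due to an AE. Its 4.6.2 definition depends on not having completed, and safety and tolerability are the primary objective.

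**Working it through.** The plan states no completion figure to reproduce, so the check is a comparison of the texts followed by one illustration.

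**Step 1: classify one child under each section.** Take a dosed child who is withdrawn because of an AE.

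| Section | Classification |
|---|---|
| Protocol 4.6.1 | Completed |
| Protocol 4.6.2, early termination | Early terminated if not a completer; cannot apply if 4.6.1 makes the child a completer |
| Protocol 4.6.2, discontinued due to an AE | Met only if the child did not complete; fails under 4.6.1 |
| Protocol Section 8 | Withdrawn, as an alternative to completed |
| Protocol 8.5 and SAP 7.1.1 | Completed and discontinued are separate counts; no rule for choosing |

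This takes the 4.6.1 sentence to cover withdrawal by the investigator or sponsor as well as by the parent, since that section deals with both. Sections 4.6.1 and 4.6.2 cannot both be applied: if withdrawal is completion, no withdrawn child is ever early terminated.

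**Step 2: follow the AE definition to the outputs.** Protocol 8.8.1 tabulates discontinuations due to an AE. SAP 7.2.2.1 and 7.2.2.2 summarize AEs leading to discontinuation from the study and list the patients concerned. If these outputs use the 4.6.2 definition together with 4.6.1 as written, children withdrawn for an AE drop out of them.

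**Step 3: see what does not change.** The Full Analysis Set is everyone who received any amount of drug (Protocol 8.3, SAP 6.1), so membership does not depend on completion. Protocol 4.6.2 has survival information on discontinued subjects collected until the study ends.

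**Step 4: illustrate the size.** Inputs:
- N = 10 treated subjects, the maximum (Protocol 8.2: "Up to 10 subjects who meet the requirements for inclusion will be enrolled in this study").
- No deaths and no losses to follow-up (assumption).
- w = 1, 2 or 3 withdrawals (assumption; the documents give no rate).

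Completion is N/N under 4.6.1 as written, and (N − w)/N if withdrawals are not completers.

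| w | 4.6.1 as written | Withdrawals not completers |
|---|---|---|
| 1 | 10/10 = 100% | 9/10 = 90% |
| 2 | 10/10 = 100% | 8/10 = 80% |
| 3 | 10/10 = 100% | 7/10 = 70% |

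Each withdrawal moves the figure by 1/N, which is 10 percentage points at N = 10 and more if fewer children are treated.

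**The case against.** The best defence is that one stray sentence stands against everything else. The eCRF records the date and reason for discontinuation, Section 8 separates completed from withdrawn, and the SAP listing gives either a completion date or a premature discontinuation date. A careful programmer would probably classify withdrawals correctly. With at most 10 children, the by-subject listing shows what happened to each one. Exposure in weeks and infusions is also reported, so no reader depends on a single percentage. The sentence looks like a drafting slip.

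Much of this stands. A reader might infer that the disposition table is certain to report withdrawals as completers. The documents do not support that. SAP 7.1.1 does not cite 4.6.1, and a withdrawn child could still appear as discontinued with a reason, or in both rows. The table is contradictory in specification and not bound to be wrong.

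A reader might also infer that completion under 4.6.1 would be 100% apart from deaths. That goes too far, because a child lost to follow-up is classified separately in 4.6.2, and 4.6.1 does not turn that into completion.

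The drafting-slip argument does not remove the problem. A lost negative and an unfinished condition are both plausible. They lead to different tables, since under a condition some withdrawals might properly count as completers. The documents do not say which was meant, and getting the right count at present means disregarding a written rule.

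**Conclusion.** The point holds as an internal contradiction that should be corrected. Protocol 4.6.1 is incompatible with 4.6.2 and with Section 8, and the SAP neither overrides it nor supplies a definition. Taken literally, it miscounts completers and removes children withdrawn for an AE from the protocol's definition of discontinued due to an AE.

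The reach is limited. A reader might suppose that the safety, efficacy or survival results are biased. They are not affected through the analysis set, and survival follow-up continues after discontinuation. The exposure is confined to disposition reporting and to any AE-discontinuation count that relies on the 4.6.2 definition. The SAP does not say whether its AE-discontinuation tables use that definition or the AE records directly, so that effect is possible but not established.

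The 90% to 70% against 100% comparison is an illustration that rests on the stated assumptions. It is not a forecast of withdrawals.

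**What to change.** 1. Correct the sentence in Protocol 4.6.1 so that a subject who withdraws prematurely is not a completer and is classed as early terminated under 4.6.2.
2. Define completed and discontinued once, as mutually exclusive categories, and use the same definition in SAP 7.1.1 and Protocol 8.5.
3. State in that definition which end of treatment, plus the follow-up visit, counts as completion. Protocol 3.2.3 gives both an expected minimum of 18 months and a maximum of 3 years, so a reference to the planned end of treatment would not be enough. The sponsor should choose between 18 months, up to 3 years, or a sponsor-defined study end. It should also say how a child still on treatment is classed if the sponsor ends the study, because 4.6.1 lists that as a reason for discontinuation.
4. If the protocol is not reopened, put the definition in SAP 7.1.1 and record the departure from 4.6.1 in SAP 4.1.

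The cost is a sentence or two in each document. Nothing changes in data collection or study conduct, because the dates and reasons are already recorded in the eCRF. It should be settled before the disposition and AE tables are programmed.
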